5. ANALYSIS POPULATIONS

5.1 ENROLLED POPULATION

The enrolled population includes all subjects who gave informed consent or assent for entry into Study ZX008-1503.

5.2 SAFETY (SAF) POPULATION

The SAF population is the set of all enrolled subjects who received at least one dose of ZX008 during the open label extension. Safety analyses will be performed on the SAF Population.

5.3 MODIFIED INTENT-TO-TREAT (MITT) POPULATION

The mITT Population is defined as all enrolled subjects who receive at least one dose of ZX008 and have at least one month (30 days) of valid seizure data during the open label extension. Effectiveness analyses, such as evaluating the change in the frequency of convulsive seizures, will be performed on the mITT Population.

6. STATISTICAL METHODOLOGY

6.1 STATISTICAL AND ANALYTICAL ISSUES

6.1.1 Statistical Methods

All data on safety, effectiveness and exploratory endpoints will be summarized. Continuous data will be summarized using descriptive statistics including number of subjects, means, standard deviations, medians, lower and upper quartiles, and ranges. Categorical variables will be summarized with frequencies and percentages.

Effectiveness and safety data may be summarized by treatment group in previous study as described in Section 3.2 in this SAP. The effectiveness and safety data will also be summarized by age group as described in Section 6.1.3, and overall.

Point and interval estimates (95% confidence intervals) will be calculated for within treatment changes from baseline for key parameters as warranted. These within-treatment changes from baseline comparisons should be interpreted with caution, as any effect of treatment may be confounded with the time-course of disease or other factors. The primary evidence for efficacy and safety of ZX008 is based on the treatment comparisons from the double-blind studies, while the data from this OLE study provides evidence of long-term safety and effectiveness.

Confidence intervals and/or p-values, where provided for between treatment group differences, should be regarded as descriptive and not for formal inferential purposes.

All descriptive statistical analyses will be performed using SAS statistical software (Version 9.3, unless otherwise noted). Adverse events will be coded using the most recent MedDRA version available at the time of analysis. Concomitant medications will be coded using the most recent version of World Health Organization (WHO) Drug.

6.1.2 Multiplicity Issues

This is an open-label extension study with no formal comparisons to be made between treatment groups defined by subjects' initial regimen in the previous study. Comparisons will be made within each treatment group comparing measurements observed during different time points in the OLE to the measurements obtained during the baseline period in the double-blind or PK study completed prior to this OLE.

Confidence intervals presented for descriptive purposes only will each have nominal 95% coverage probability.

No formal adjustment for multiplicity is made.

6.1.3 Subgroups

Effectiveness and select safety data may be further broken down by the following subgroups:

- Age strata (based on age at informed consent at core study entry or entry de novo): 2 to <6 years, $\geq 6 - 18$ years.
- Region: Countries may be grouped into two regions: North America (US/Canada), Rest-of-World (ROW).
- Japan: Subjects enrolled from Japan are considered as a separate subgroup.

6.1.4 Definitions

6.1.4.1 Baseline (Core)

For de novo subjects, the baseline (core) is undefined. For other subjects, the baseline (core) is defined as follows.

For effectiveness endpoints (excluding seizure), the baseline (core) will be defined dependent on their core study. For subjects from ZX008-1501, ZX008-1502, or ZX008-1504 Cohort 2, baseline (core) is the last value prior to randomization in the preceding double-blind study. For subjects from ZX008-1504 Cohort 1, baseline (core) is the last value prior to the start of PK dosing and assessments. For De Novo subjects, the baseline is the last value prior to dosing in ZX008-1503.

For all subjects in Study ZX008-1501, Study ZX008-1502, or Study ZX008-1504 Cohort 2, the baseline (core) period is equivalent to the core study pre-randomization period, i.e., the approximately 42-day span just prior to randomization and start of treatment in the core study. The baseline (core) seizure frequency will be based on the information collected from their daily diaries during the baseline period (lasting approximately 42 days).

For subjects from Study ZX008-1504 Cohort 1 the baseline (core) for efficacy rating scales (e.g. questionnaires) will be the last rating prior to start of dosing in the Core Study. Baseline seizure frequency for Study ZX008-1504 Cohort 1 will not be calculated.

6.1.4.2 *Baseline (OLE)*

Baseline (OLE) value for the Open-label treatment period is defined as the last assessment on or before the start of the OLE period. In most cases, (though not seizure frequency) this will be the value obtained at Visit 1 (Study Day 1) of Study ZX008-1503.

Thus, Baseline (OLE) lab, vital signs, ECG, ECHO, assessments refer to the assessments obtained on this day, as does Baseline (OLE) value for effectiveness endpoints with the exception of seizures.

For de novo subjects, the baseline (OLE) seizure frequency will be based on the information collected from their daily diaries during the baseline period (lasting approximately 28 days) prior to first dose in ZX008-1503.

6.1.4.3 *Open-Label Extension (OLE) Treatment Period*

The OLE Treatment Period covers the 36 months during which subjects will receive open label treatment with ZX008.

For each subject, OLE day 1 (OLED1) is the subject's first day of dosing in the OLE period. Study day for 1503 begins with OLED1.

6.1.4.4 *Post-dosing Period*

The Post-dosing Period begins immediately at the end of OLE Treatment Period and extends for 2 weeks.

6.1.4.5 *Follow-up Period*

Subjects are to return for an ECHO and ECG assessment 3 and 6 months after the end of the study. The follow-up period begins the day after Visit13 and ends with Visit15.

6.1.5 *Other Definitions*

6.1.5.1 *Phase and Study Day Definitions*

The analyses will require definition of 3 Phases: Pre-OLE, OLE, and Post-OLE.

- The pre-OLE Phase comprises (1) the baseline (Core) period, (2) the Core Study (CS) period (including the transition period in the core study)
- The OLE Phase starts from dosing on OLED1 and comprises (1) the OLE Treatment Period, and (2) the Taper Period. The last day of the OLE phase is the date of Visit 17.
- The post-OLE phase begins one day after the date of Visit 17 in 1503 and ends with the date of Visit 19.

Study Day 1 is the date of first dose in the OLE Study. In most cases, this will be the date of Visit 1 or the day after that date.

6.1.6 *Visit Windows and Period Start/Stop Dates*

The following definitions of phase and period will be used:

Table 6. Definition of Phase/Period

Phase	Period	Description
Pre-OLE Phase	Baseline (Core) Period	This description here applies to all subjects except the de novo subjects. This period refers to the period prior to the beginning of the double-blind period in the Core study. The Baseline (Core) period start date is the date of Visit 1 in the Core study. The Baseline (Core) period end date is the date of Visit 3/randomization in the Core study. For subjects in Study ZX008-1504 (Cohort 1), the baseline period starts and ends on the date of Visit 1.
Pre-OLE Phase	Core Study Period	This description here applies to all subjects except the de novo subjects. The start date of this period is the date of randomization or first dose in the Core (double-blind) study, whichever occurs first. The end date of this period is the last date the subject was on study treatment. For subjects entering Study ZX008-1503 who completed Core studies ZX008-1501, ZX008-1502 or ZX008-1504 Cohort 2, this will be the date of Visit 13 in the core study. For subjects who discontinue early from the Core study, the Core study period end date is the latest assessment date for that study. For subjects entering ZX008-1503 who were in ZX008-1504 Cohort 1, this will be the date of the Visit 17 assessment in Study 1504 Cohort 1 (for those who completed), or the date of the latest assessment date (for those who discontinued ZX008-1504 Cohort 1 prematurely but were allowed entry into 1503, if any).
Pre-OLE Phase	Baseline (OLE) Period – de novo subjects	This description here applies to the de novo subjects. This start date of this period be the date of screening. The end date of the period will be the last date prior to the first dose of study drug in Study ZX008-1503.
OLE Phase	OLE Treatment Period	The OLE Treatment Period consists of the 36-month period from Visit 1 of the OLE study through Visit 16 of the OLE study The OLE Treatment Period start date is the date of first dose in Study ZX008-1503. The OLE Treatment Period end date is the date of end of study visit, Visit 16/ET. For subjects who discontinue early from the study, the OLE Treatment Period end date will be the date of the ET visit - safety measures collected at the last clinic visit will be used even in the event that study drug was discontinued prior to the date of the visit. Note: Adverse events occurring up to Visit 17 are regarded as occurring during treatment. In addition, AEs occurring up to 30 days after the last dose date will be regarding as treatment emergent.
OLE Phase	Taper Period	The Taper period consists of 2 weeks starting from end of study/early termination visit (Visit 16) + 1 day. The end date of this period is the date recorded for Visit 17.
Post-OLE Phase	Post-OLE Period	The start date of the post-OLE period is the date of Visit 17, + 1 day for subjects who complete the OLE Treatment period, or the day after the date of end of taper, for subjects who discontinue early. [There is not explicit end date for the post-OLE Phase. However, if needed, this may be set to be 45 days after the date of Visit 19, or V17 date + 210.]

For the purpose of statistical analysis, visit windows around the target visit dates will be implemented to capture effectiveness and/or safety data within similar periods. These windows are distinct from the

permissible visit scheduling windows specified in the Visit Schedule in the protocol that are used for the conduct of the study.

The following rules will be used to window data into treatment periods for tabulations that are generated by time during the OLE Treatment period.

Table 7a. Time Intervals for Analysis Visits for Seizure Analysis*

Analysis Phase/Period	Scheduled Visit Number in ZX008-1503	Analysis Visit**	Time Interval (label on output)	Time Interval (Day)
Pre-OLE	N/A	-99	Baseline (Core)*	Core Study Day -42 to Day-1 of Core Study
Pre-OLE	N/A	-9	Core Study (T+M)*	Day 1 of Core Study to End of T+M in Core Study
Pre-OLE	N/A	-1	Core Study Final * Week	End of T+M in Core Study – 6 days, to End of T+M in Core Study
Pre-OLE de novo	N/A	-99	Baseline (OLE)*	Day -28 to Day -1 of Study ZX008-1503
OLE	3	1	Month 1 (OLE)	1-30
OLE	4	2	Month 2 (OLE)	31-60
OLE	5	3	Month 3 (OLE)	61-90
OLE	6	4	Month 4-6 (OLE)	91-180
OLE	7	5	Month 7-9 (OLE)	181-270
OLE	8	6	Month 10-12 (OLE)	271-360
OLE	9	7	Month 13-15 (OLE)	361-450
OLE	10	8	Month 16-18 (OLE)	451-540
OLE	11	9	Month 19-21 (OLE)	541-630
OLE	12	10	Month 22-24 (OLE)	631-730
OLE	13	11	Month 25-27 (OLE)	731-820
OLE	14	12	Month 28-30 (OLE)	821-910
OLE	15	13	Month 31-33 (OLE)	911-1000
OLE	16	14	Month 34-36 (OLE)	1001-1095
OLE	NA	99	Month 01-EOS (ENDPT1)	1 to min(Last Dose date, Visit 16 date)
OLE	NA	98	Month 02-EOS (ENDPT2)	31 to min(Last Dose date, Visit 16 date)

Note: EOS/ET date = Visit 16 date. Per protocol, Visit 17 is end of the OLE Phase.

T+M=Titration + Maintenance in Core Study.

*Subjects in Study ZX008-1504 Cohort 1 will not have a baseline(core), For those subjects, the Core Study(T+M) represents all their seizure data during the transition period in the core study. Their core study final week will be the last 7 days of seizure data prior to the first visit in ZX008-1503. De novo subjects start Study ZX008-1503 treatment after a screening period.

**Analysis visit numbers are not the same as nominal visit numbers.

Table 7b. Time Intervals for Questionnaires*

Analysis Phase/Period	Scheduled Visit Number in ZX008-1503	Analysis Visit Number*	Time Interval (label on output)	Time Interval (Day)	Target Time Point (Day)
Pre-OLE	N/A	-99	Baseline (Core)	<1	Core Study Day -42 to Day-1 of Core Study
Pre-OLE	1	1	Baseline (OLE)	1	1
OLE	3	3	Month 1 (OLE)	21 to 44	30
OLE	4	4	Month 2 (OLE)	45 to 74	60
OLE	5	5	Month 3 (OLE)	75 to 134	90
OLE	6	6	Month 6 (OLE)	135 to 224	180
OLE	7	7	Month 9 (OLE)	225 to 314	270
OLE	8	8	Month 12 (OLE)	315 to 409	365
OLE	9	9	Month 15 (OLE)	410 to 499	455
OLE	10	10	Month 18 (OLE)	500 to 589	545
OLE	11	11	Month 21 (OLE)	590 to 679	635
OLE	12	12	Month 24 (OLE)	680 to 774	730
OLE	13	13	Month 27 (OLE)	775 to 864	820
OLE	14	14	Month 30 (OLE)	865 to 954	910
OLE	15	15	Month 33 (OLE)	955 to 1044	1000
OLE	16	16	Month 36 (OLE)	1045 to 1109	1095
OLE	OLE Last Visit**	99	Last Value	Day 2 to Visit 17 date	

*For multiple measurements within a time window, please use the closest to the target time point. Note that measurements occurring on the end date of a phase/period or start date of a new phase/period are assigned to the preceding phase/period. For example, measurements taken on OLE Study Day1 are assigned as Baseline (OLE).

**The last observation in the time window will be used. [This is an exception from the rule in the preceding note.]

Table 7c. Time Intervals for Analysis Visits for Laboratory Data and Vital Signs*

Analysis Phase/Period	Scheduled Visit Number in ZX008-1503	Analysis Visit Number*	Time Interval (label on output)	Time Interval (Day)	Target Time Point (Day)
Pre-OLE	1	1	Baseline (OLE)	1	1
OLE	2	2	Week 2 (OLE)	2 to 20	15
OLE	3	3	Month 1 (OLE)	21 to 44	30
OLE	4	4	Month 2 (OLE)	45 to 74	60
OLE	5	5	Month 3 (OLE)	75 to 134	90
OLE	6	6	Month 6 (OLE)	135 to 224	180
OLE	7	7	Month 9 (OLE)	225 to 314	270
OLE	8	8	Month 12 (OLE)	315 to 409	365
OLE	9	9	Month 15 (OLE)	410 to 499	455
OLE	10	10	Month 18 (OLE)	500 to 589	545
OLE	11	11	Month 21 (OLE)	590 to 679	635
OLE	12	12	Month 24 (OLE)	680 to 774	730
OLE	13	13	Month 27 (OLE)	775 to 864	820

Analysis Phase/Period	Scheduled Visit Number in ZX008-1503	Analysis Visit Number*	Time Interval (label on output)	Time Interval (Day)	Target Time Point (Day)
OLE	14	14	Month 30 (OLE)	865 to 954	910
OLE	15	15	Month 33 (OLE)	955 to 1044	1000
OLE	16	16	Month 36 (OLE)	1045 to 1109	1095
OLE	OLE last Visit**	99	Last Value	Day 2 to Visit 17 date	

*For multiple measurements within a time window, please use the closest to the target time point. Note that measurements occurring on the end date of a phase/period or start date of a new phase/period are assigned to the preceding phase/period. For example, measurements taken on OLE Study Day1 are assigned as Baseline (OLE).

**The last observation in the time window will be used. [This is an exception from the rule in the preceding note.]

Table 7d. Time Intervals for Analysis Visits for Tanner Staging*

Analysis Phase/Period	Scheduled Visit Number in ZX008-1503	Analysis Visit Number*	Time Interval (label on output)	Time Interval (Day)	Target Time Point (Day)
Pre-OLE	1	1	Baseline (OLE)	1	1
OLE	2	2	Week 2 (OLE)	2 to 20	15
OLE	3	3	Month 1 (OLE)	21 to 44	30
OLE	4	4	Month 2 (OLE)	45 to 74	60
OLE	5	5	Month 3 (OLE)	75 to 134	90
OLE	6	6	Month 6 (OLE)	135 to 224	180
OLE	7	7	Month 9 (OLE)	225 to 314	270
OLE	8	8	Month 12 (OLE)	315 to 409	365
OLE	9	9	Month 15 (OLE)	410 to 499	455
OLE	10	10	Month 18 (OLE)	500 to 589	545
OLE	11	11	Month 21 (OLE)	590 to 679	635
OLE	12	12	Month 24 (OLE)	680 to 774	730
OLE	13	13	Month 27 (OLE)	775 to 864	820
OLE	14	14	Month 30 (OLE)	865 to 954	910
OLE	15	15	Month 33 (OLE)	955 to 1044	1000
OLE	16	16	Month 36 (OLE)	1045 to 1109	1095
OLE	17/OLE Last Visit**	99	Last Value	Day 2 to Visit 17 date	

*For multiple measurements within a time window, please use the closest to the target time point. Note that measurements occurring on the end date of a phase/period or start date of a new phase/period are assigned to the preceding phase/period. For example, measurements taken on OLE Study Day1 are assigned as Baseline (OLE). Visits where the Tanner Stage is not scheduled for collection are included due to early termination visits occurring between scheduled visits.

**The last observation in the time window will be used. [This is an exception from the rule in the preceding note.]

Table 7e. Time Intervals for ECGs and ECHO*

Analysis Phase/Period	Scheduled Visit Number in ZX008-1503	Analysis Visit*	Time Interval (label on output)	Time Interval (Day)	Target Time Point (Day)
Pre-OLE	1	1	Baseline (OLE)	<1	1
OLE	3	3	Month 1 (OLE)	2 to 44	30
OLE	4	4	Month 2 (OLE)	45 to 74	60
OLE	5	5	Month 3 (OLE)	75 to 134	90
OLE	6	6	Month 6 (OLE)	135 to 224	180
OLE	7	7	Month 9 (OLE)	225 to 314	270
OLE	8	8	Month 12 (OLE)	315 to 409	365
OLE	9	9	Month 15 (OLE)	410 to 499	455
OLE	10	10	Month 18 (OLE)	500 to 589	545
OLE	11	11	Month 21 (OLE)	590 to 679	635
OLE	12	12	Month 24 (OLE)	680 to 774	730
OLE	13	13	Month 27 (OLE)	775 to 864	820
OLE	14	14	Month 30 (OLE)	865 to 954	910
OLE	15	15	Month 33 (OLE)	955 to 1044	1000
OLE	16	16	Month 36 (OLE)	1045 to 1109	1095
OLE	17/Final Visit**	99	Last Value	2 to Visit 17 date	
Post-OLE	18	999	Cardiac FU 1	Visit 17 date + 1, to Visit 18 date	
Post-OLE	19	9999	Cardiac FU 2	Visit 18 date +1, to Visit 19 date	

*For multiple measurements within a time window, please use the closest to the target time point. Note that measurements occurring on the end date of a phase/period or start date of a new phase/period are assigned to the preceding phase/period. For example, measurements taken on OLE Study Day1 are assigned as Baseline (OLE).

** The last observation in the time window will be used. [This is an exception from the rule in the preceding note.]

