AED=antiepileptic drug; BMI=body mass index; BRIEF=Behavior Rating Inventory of Executive Function; C=Collect; CBD=cannabidiol; CGI-I=Clinical Global Impression-Improvement; D=Dispense; ECG=electrocardiogram; EOS=end of study; ET=early termination; EQ-5D-5L=standardized measure of health status; HADS=Hospital Anxiety and Depression Scale; PedsQL=Pediatric Quality of Life Inventory; QoL=quality of life; QOLCE=Quality of Life in Childhood Epilepsy; R=Review

NOTE: If a subject has a birthday during the study that makes a previously unrequired assessment now required (eg, Tanner staging in a male subject who turns 8 years old during the study), this assessment(s) should be initiated at visits subsequent to the birthday.

**** de Novo subjects are subjects who did not participate in one of the core studies and may or may not be currently taking STP.**

- a: For subjects enrolling from one of the core studies use data collected at Visit 12 and Visit 13 of Study ZX008-1501 or ZX008-1502.
For de novo subjects, a screening period up to 28 days is required. During this period, informed consent is required prior to any study-related procedures. All results to determine eligibility must be reviewed prior to receiving the first dose of study medication at Visit 1.
For all subjects, clinical laboratory results and all ECHO/ECG results must be available and meet eligibility criteria prior to receiving the first dose of study medication at Visit 1.
- b: De Novo subjects must meet entry criteria 3 to 7, and 10, including having had ≥ 4 convulsive seizures (tonic, tonic-atonic, tonic-clonic, clonic) per 4-week period for past 12 weeks prior to screening, by parent/guardian report to investigator or investigator medical notes.
- c: At the discretion of the investigator, Visit 2 may be conducted as a phone visit.
- d: Or early termination.
- e: Follow-up ECG, ECHO, and physical examination will be performed 3 and 6 months after study completion or early termination.
- f: For subjects enrolling from one of the core studies, use core study Visit 12 information unless complete neurological examination is warranted based on significant changes in subject status.
- g: ECHOs will be performed at Months 1, 3, 6, 9, 12, 15, 18, 21, 24, 27, 30, and 33.

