- h: The Months 3, 6, 9, 12, 15, 18, 21, 24, 27, 30, and 33 ECHO may be performed any time within 3 weeks prior to the study visit. If a subject discontinues early from the study, the ECHO should be scheduled as soon as practical (see Table 7).
- i: Females of child-bearing potential
- j: For subjects enrolling from one of the core studies, use data collected at Visit 12 of ZX008-1501 or ZX008-1502 for Visit 1 unless clinical laboratory evaluation is warranted based on significant changes in subject status. Visit 2 clinical laboratory evaluation is optional based on subject status for all cohorts.
- k: Months 6, 15, and 27 only.
- l: Visits 3 and 4 (Months 1 and 2) only.
- m: Only adverse events related to cardiac safety will be collected at this visit (see Table 7).
- n: Not to be completed for de novo subjects >18 years old.

Table 5. Schedule of Assessments for Subjects from Core Study ZX008-1504

Study Assessments	OLE Treatment Period				Post-Dosing	Cardiac Follow-up	
	Visit 1 ^a	Visit 2 ^b		Visits 3-15 (Months 1, 2, 3, 6, 9, 12, 15, 18, 21, 24, 27, 30, and 33)			Visit 16 ^c (EOS/ET) Month 36
Study Day	1 ^a	15		30, 60, 90, 180, 270, 365, 455, 545, 635, 725, 815, 905, 995	1085	1099	3 and 6 months post last dose
		Clinic	Phone				
Informed Consent	X						
Entry Criteria	X						
Demographics	X						
Medical/Neurological History	X ^a						
Epilepsy History	X ^a						
Physical Examination, complete	X ^a				X		X ^d
Physical Examination, abbreviated		X		X			X ^d
Neurological Examination, complete	X ^c				X		
Neurological Examination, abbreviated		X		X			
Vital signs	X	X		X	X		
Weight, Height, BMI	X ^a	X		X	X		
12-lead ECG	X ^a			X	X		X ^d
Doppler ECHO	X ^a			X ^{f,g}	X		X ^d
Urine Pregnancy Test ^h	X			X	X		
Clinical laboratory evaluation (hematology/clinical chemistry/urinalysis, etc)	X ⁱ	X ⁱ		X	X		
Urine THC Panel/Whole blood CBD	X ^a			X	X		
Plasma sample for background AEDs		X		X	X		
Tanner Staging (for subjects > 7 years old)	X ^a			X ^j	X		X ^j
C-SSRS	X ^a			X	X		
CGI-I (assessed by parent/caregiver)	X ^a			X	X		
CGI-I (assessed by principal investigator)	X ^a			X	X		
QOLCE	X ^a			X	X		
EQ-5D-5L (QoL of parent/caregiver)	X ^a			X	X		
BRIEF	X ^a			X	X		
Healthcare utilization questions	X ^a			X	X		

continued

Table 5. Schedule of Assessments for Subjects from Core Study ZX008-1504 (continued)

Study Assessments	OLE Treatment Period				Post-Dosing	Cardiac Follow-up	

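### The Day-1-only laboratory baseline in SAP Section 6.1.4.2 and Table 7c contradicts the schedule, which normally places that sample before Day 1, and the SAP's own general definition of Baseline (OLE)

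*SAP*

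**What the plan says.** Section 6.1.4.2 makes two statements. The general one is that Baseline (OLE) "is defined as the last assessment on or before the start of the OLE period", usually the Visit 1 value. The specific one follows directly: "Baseline (OLE) lab, vital signs, ECG, ECHO, assessments refer to the assessments obtained on this day".

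The window table for these data in Section 6.1.6, "Table 7c. Time Intervals for Analysis Visits for Laboratory Data and Vital Signs", follows the specific statement. Its baseline row gives interval 1 and target 1 ("Baseline (OLE) 1 1") and the next row starts on Day 2 ("Week 2 (OLE) 2 to 20 15"). The same table is reprinted for programmers in the TLF shells, ahead of Table 14.3.4.1.

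The schedule in Section 4 describes a different sample. For roll-over subjects from 1501 and 1502, Table 4 footnote j says to "use data collected at Visit 12 of ZX008-1501 or ZX008-1502 for Visit 1 unless clinical laboratory evaluation is warranted" by an important change in the subject's condition. Table 5 footnote i sends 1504 Cohort 2 to core Visit 12 and Cohort 1 to the last transition-period visit, with the same exception. De novo subjects have up to 28 days of screening, and Table 4 footnote a requires that "clinical laboratory results and all ECHO/ECG results must be available and meet eligibility criteria prior to receiving the first dose". Table 4 itself dates Visit 1 as Study Day −28 to 1.

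For ECG and ECHO, Table 7e gives the baseline interval as <1 and starts Month 1 at Day 2. The footnote under Tables 7b to 7e adds: "For example, measurements taken on OLE Study Day1 are assigned as Baseline (OLE").

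**The concern.** Long-term safety is the primary objective, and Section 6.4.9 plans change from baseline for every continuous laboratory parameter. That needs a baseline value for each subject. If a programmer applies the Table 7c row as printed, the sample that the schedule designates as the baseline is excluded by rule.

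The subjects who keep a baseline would be mainly those resampled on Day 1, and the only reason the SAP gives for resampling is a significant change in status. The change-from-baseline summaries could then describe a selected group, and nothing in the table titles would show it.

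Weight shares part of the problem. Section 6.4.5 handles it with vital signs, and its Visit 1 entry carries footnote a, so the value comes from core Visits 12 and 13 or from screening. The weight-loss and weight-gain percentages in Table 14.4.1.5 use subjects with a baseline weight as the denominator, so a subject without one drops out silently.

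**Working it through.** No sample-size, power or event figure underlies this point. The check sets the day of the scheduled sample against the printed windows.

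**1. When the scheduled baseline sample is taken.**
- 1501, 1502 and 1504 Cohort 2: core Visit 12. Section 3.2 places the transition period between Visits 12 and 13, so Visit 12 precedes OLE Day 1.
- 1504 Cohort 1: the last visit of the transition period. The notes to Table 14.2.1.1.5 end that period one day before OLE Day 1.
- De novo: screening, Day −28 onward, with results in hand before the first dose.
- Any subject: Section 6.1.5.1 allows Day 1 to be the day after Visit 1, so even a fresh Visit 1 value can fall on Day −1.

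**2. Which window each day falls in, taking the interval columns literally.**

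| Study day | Table 7c (laboratory, vital signs) | Table 7e (ECG, ECHO) |
|---|---|---|
| −28, −15, −14, −7, −1 | none | Baseline (OLE) |
| 1 | Baseline (OLE) | none by interval; baseline by footnote |
| 2, 15 | Week 2 | Month 1 |

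Table 7c drops every day before Day 1, which is where step 1 puts the scheduled laboratory sample. Table 7e has the opposite gap, at Day 1 itself, but its footnote closes it.

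**3. Which outputs depend on it.** The Table 14.3.4.1 shell reports change from baseline and is reused for biochemistry (14.3.4.2), quantitative urinalysis (14.3.4.4.1) and the growth, puberty and thyroid tests (14.3.4.5). Its note refers the reader to the SAP for the windows. Categorical urinalysis (14.3.4.4.2) reports counts by visit only, so no change score is lost there.

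**4. With the general definition in the baseline row.** If the row read as the last value on or before Day 1, every tested day from −28 to 1 would map to Baseline (OLE), and the windows from Day 2 would not move.

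**The case against.** The strongest reply is that the SAP already contains the right rule. The first sentence of 6.1.4.2 accepts values before Day 1, and its wording foresees exceptions to Visit 1. Footnote j designates the core Visit 12 data as the Visit 1 value, and the Table 7c baseline row is keyed to scheduled Visit 1 in the Pre-OLE phase, so mapping carried-over data to that row is a natural reading. Table 6 gives de novo subjects a Baseline (OLE) period running from screening to the day before first dose. Section 6.1.6 also says that the windowing rules serve tabulations by time during OLE treatment.

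Most of this stands, and it rules out saying that the baselines will be lost. It does not settle the matter. The sentence restricting the baseline to that day names laboratory data and agrees with Table 7c. The interval column prints 1, whereas Table 7e prints <1 where days before Day 1 are meant. The SAP does not say which statement prevails, so two programmers could derive different baselines from it.

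A reader might also infer an equal and opposite error for ECG and ECHO. The documents do not support that. The Table 7e footnote assigns Day 1 to baseline, its target day is 1, scheduled readings before Day 1 fit the printed interval, and Sections 6.4.6 and 6.4.7 leave reporting to separate vendor reports.

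A reader might take the counts in the categorical urinalysis shell as a measure of the loss. That shell is marked as illustrative and has no change-from-baseline output, so it measures nothing here.

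**Conclusion.** The contradiction is real and should be corrected. Section 6.1.4.2 and Table 7c restrict the laboratory baseline to Day 1, while the schedule normally places that sample before Day 1 and the SAP's own general definition accepts it there. On the literal reading, continuous laboratory change from baseline would rest mainly on subjects resampled on Day 1. Weight taken from core Visit 12 or screening, and any Visit 1 value when the first dose is given the next day, has the same exposure. Other vital signs have no carry-over footnote at Visit 1 and are exposed only in that next-day case.

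The loss is conditional on Table 7c and the specific sentence overriding the general one. Its size cannot be computed, because the SAP gives no count of subjects resampled on Day 1; for the same reason, the selected subset is a possibility that the SAP does not establish. A reader might conclude that all subjects, or all laboratory tables, lose their baseline, and neither follows from the text. The ECG and ECHO wording is a minor inconsistency.

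**What to change.** In Table 7c and its copy in the TLF shells, define Baseline (OLE) as the last non-missing value on or before the first OLE dose (Day 1). State that carried-over core Visit 12 and 13 values, the last Cohort 1 transition-visit value and de novo screening values qualify. In Section 6.1.4.2, delete the sentence that ties these baselines to that day, or align it with the general definition. As a minor consistency edit, change the Table 7e baseline interval from <1 to on or before Day 1, to match its footnote. Table 7d prints the same Day-1-only row for Tanner staging and can be aligned at the same time.

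The cost is SAP wording and one derivation rule. The schedule already calls for the core values as Visit 1 data, and no later window changes. The drawback is that the age of the baseline value will vary between subjects, so the laboratory and weight tables should report the median number of days from the baseline value to Day 1.
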